8.3.6 Adverse Events of Special Interest

Adverse Events of Special Interest (AESI) for this study include:

- AEs of possible remote spread effect of toxin
- AEs suggestive of hypersensitivity reaction.

These events must be collected in the eCRF.

If they meet the seriousness criteria, they should also be reported as SAEs (refer to Appendix 10.3).

Adverse events of special interest are AEs that may not be serious but are of special importance to a particular drug or class of drugs. Such events might be precursors to more serious medical conditions, for example, muscle pain and elevated creatine phosphokinase may be indicative of potential rhabdomyolysis.

Other types of nonserious events may be important in and of themselves, such as those that could affect quality of life in a meaningful way (e.g. impotence, hair loss).

Adverse events of special interests with BoNT are events that suggest a possible remote spread effect of the toxin and are presented by function in Section 10.4 (Appendix 4). These symptoms could be related to toxin spread and in case of occurrence they should be reported and monitored carefully until resolution. AEs suggestive of hypersensitivity reaction are also of special interest and will be analysed using the Medical Dictionary for Regulatory Activities (MedDRA) Hypersensitivity standardised MedDRA queries (SMQ) (narrow). All AEs will be monitored by the sponsor to determine if they meet the criteria of AESIs.

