5.8.3 Adverse Event

All Adverse Events (AEs) recorded in the eCRF will be coded using the latest version of MedDRA dictionary effective within IPSEN at the time of the database lock. AEs will be classified as Treatment-Emergent AEs (TEAEs) according to the rules below:

- Events with start date and time on or after the date and time of IMP administration,
- Events whose intensity increased on or after the date and time of IMP administration,

Refer to [Appendix A1](#) for handling of partial date. In the case where it is not possible to define an AE as treatment emergent or not, the AE will be classified by the most conservative case, i.e. treatment-emergent.

The following summaries will be provided:

- An overview table summarizing the
 - number and percentage of participants with at least one of the following AEs: any AE; any TEAE; TEAEs by intensity; TEAE by causality; AESIs by type of AESI (hypersensitivity and Remote Spread of Toxin AESIs), related and not related Serious Adverse Event (SAE), treatment-emergent SAE, TEAE leading to discontinuation from the study,
 - corresponding number of events for each of the AE categories listed above,
- A summary of the number and percentage of participants reporting at least one TEAE and the number of events, by study intervention group, SOC and PT,
- A summary of the number and percentage of participants reporting at least one treatment related AE and the number of events, by study intervention group, SOC and PT,
- A summary of the number and percentage of participants reporting at least one TEAE and the number of events, by study intervention group, by decreasing overall frequency of PT.

AEs summaries will be ordered in term of decreasing frequency for SOC and PT within SOC in overall participants and then alphabetically for SOC and PT within SOC.

In the overall summary, only the final adjudicated list of Remote Spread of Toxin AESIs confirmed by the sponsor as “a possible remote spread event” will be included.

In summary presentations, AEs will be counted as follows:

- Participants with more than one AE within a particular SOC are counted only once for that SOC. Similarly, participants with more than one AE within a particular PT are counted only once for that PT;
- Participants reporting a TEAE more than once within that SOC/ PT, the TEAE with the worst-case relationship to study medication (order: related > not related > missing) will be used in the corresponding relationship summaries;

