- If the causality is missing for a TEAE, it will be considered related in the summary tables.

In addition, a listing with all AEs data will be listed by study intervention group including non-TEAEs, Treatment-emergence status will be flagged in the listing.

A specific listing will be performed for treatment-related AEs.

Deaths, SAEs, and Other Significant Adverse Events (AE)

AESIs for Dysport are TEAEs that suggest a possible remote spread of effect of the toxin or events suggestive of hypersensitivity-like reactions.

- TEAEs due to possible remote spread of the effects of Dysport will be identified using the list of MedDRA PTs compatible with the mechanism of action of Dysport and based on the FDA.
- TEAEs potentially representing hypersensitivity reactions will be identified using the Standardised MedDRA Query (SMQ) (narrow search query) for hypersensitivity reactions.

The list of MedDRA preferred terms, used to identify any potential AESI, is provided in the data review plan.

All potential Remote Spread of Toxin AESIs identified using the search strategy described above will be medically evaluated during the study, before the database lock and unblinding, by the sponsor to identify events which could possibly represent 'remote spread of effect of toxin' due to study treatment administration. Potential Remote Spread of Toxin AESIs will be excluded if they are confounded by presence of alternative clinical aetiologies (medical history, concomitant medication or diagnosis which could account for the symptoms); if they are considered to be local effects instead of remote spread of toxin as judged by the site of injection; the time period between the last study treatment administration and event onset is not in accordance with the expected mechanism of action; or due to insufficient information/evidence to make an assessment.

The following summary tables on AESIs will be performed:

- AESIs with the number and percentage of participants and the number of events presented by study intervention group, by primary SOC and PT, presented by type of AESI (hypersensitivity and Remote Spread of Toxin AESIs).
- In addition, a table of pre-adjudicated potential Remote Spread of Toxin events will be produced for transparency and traceability by study intervention group and by primary SOC and PT.

The following listings will be provided:

- A listing of all deaths that occurred during the study,
- A listing of all SAEs,

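### Possible remote-spread events that cannot be assessed drop out of the adjudicated AESI count and cannot be told apart from events that were ruled out

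*SAP*

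**What the plan says.** Protocol 8.3.6 describes the botulinum toxin AESIs as "events that suggest a possible remote spread effect of the toxin" and attaches no exclusion for poor documentation. AESIs are a listed safety endpoint in Protocol section 3 and SAP 2.1.1. Protocol 2.2 names distant spread as the risk inherent to the class.

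SAP 5.8.3 turns this into a two-step process. Candidates are found by a preferred-term search. They then "will be medically evaluated during the study, before the database lock and unblinding, by the sponsor", and the stated purpose is "to identify events which could possibly represent 'remote spread of effect of toxin' due to study treatment administration". A candidate is excluded on any of four grounds:

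1. another clinical cause could account for it;
2. it is a local rather than a remote effect;
3. its onset does not fit the mechanism of action;
4. "or due to insufficient information/evidence to make an assessment".

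For the overview table, "only the final adjudicated list of Remote Spread of Toxin AESIs confirmed by the sponsor" as possible spread are included. The same section adds that "a table of pre-adjudicated potential Remote Spread of Toxin events will be produced for transparency and traceability", by arm, system organ class and preferred term.

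Two other defaults in 5.8.3 deal with missing information. Where treatment emergence cannot be determined, "the AE will be classified by the most conservative case, i.e. treatment-emergent". For relatedness, "If the causality is missing for a TEAE, it will be considered related in the summary tables".

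**The concern.** Grounds 1 to 3 each say something about the event: another cause, a local effect, the wrong timing. Ground 4 says something about the file. An event that matched the search and cannot be assessed has not been shown to be anything other than possible spread, yet it gets the same outcome as an event that has been explained.

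At stake is how the main AESI figure is read. A zero for remote spread in the overview could mean that every candidate was explained, or that some could not be judged. These are different safety statements in healthy volunteers who, as Protocol 2.2 says, have no benefit from taking part. As the outputs are described, a reader cannot tell which one applies.

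**Working it through.** The plan states no AESI rate or count, so there is no figure to reproduce. The check is first of logic, then of scale.

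**Step 1: each ground against the standard.** The standard is possible spread (Protocol 8.3.6; SAP 5.8.3).

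| Ground in SAP 5.8.3 | What must be shown | Evidence against possible spread? |
|---|---|---|
| Alternative cause | history, medication or diagnosis that could explain the event | yes |
| Local effect | relation to the injection site | yes |
| Timing | onset not in keeping with the mechanism | yes |
| Insufficient information | nothing | no |

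**Step 2: what can be recovered from the planned outputs.** For one arm, counting events, let P = candidates before adjudication, C = sponsor-confirmed events, A, L and T = events excluded on grounds 1 to 3, and U = events excluded as unassessable. Then

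P = C + A + L + T + U, so P − C = A + L + T + U.

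The pre-adjudication table gives P and the overview gives C. U is known only to lie between 0 and P − C. The number of events not shown to be something else is C + U, which can lie anywhere from C to P. SAP 5.8.3 does not say that the table or any AE listing will carry the adjudication outcome or reason. The output shells are a separate document and might add it, but the SAP does not require it.

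**Step 3: scale, as an illustration.** Inputs: 15 participants per arm (SAP 2.3), all assumed dosed. Assume no confirmed event and k participants in one arm, each with one unassessable candidate. Exact (Clopper-Pearson) two-sided 95% limits for k of n are

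lower = Beta quantile 0.025 (k, n − k + 1); upper = Beta quantile 0.975 (k + 1, n − k).

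For k = 0 the upper limit is 1 − 0.025^(1/15) = 21.8%.

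| k | Confirmed count under the present rule | Confirmed plus unassessable |
|---|---|---|
| 1 | 0/15 = 0% (0 to 21.8%) | 1/15 = 6.7% (0.2 to 31.9%) |
| 2 | 0/15 = 0% (0 to 21.8%) | 2/15 = 13.3% (1.7 to 40.5%) |
| 3 | 0/15 = 0% (0 to 21.8%) | 3/15 = 20.0% (4.3 to 48.1%) |

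Each affected participant is 1/15 = 6.7 percentage points of an arm, or 1/45 = 2.2 points of the study. The intervals only show how little 15 participants can exclude; SAP 5.8.3 plans counts and percentages for AESIs.

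**The case against.** There is a good deal on the other side, and most of it stands as a limit on the point.

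- **The events remain visible.** A reader might infer that unassessable events vanish or are reported as non-AESIs. The SAP does not support that. They appear by arm in the pre-adjudication table and, as TEAEs, in the TEAE tables and the full AE listing. They leave the adjudicated count only.
- **Adjudication adds specificity.** A reader might infer that the overview count is biased downwards. That is not shown. An event with too little information is not known to be spread, and Protocol Appendix 4 includes non-specific terms such as constipation, dry mouth and muscular weakness. Counting every unassessable event as confirmed could overstate the risk. Publishing a sensitive count and a specific one is a legitimate design.
- **The SAP has no uniform conservative rule.** The two defaults quoted above run the other way from ground 4, and a reader might infer a breach of a SAP-wide principle. But the worst-case order for relationship in 5.8.3 ranks missing below not related. That order only chooses among several events in one participant and removes none, but it shows that no such principle is applied throughout.
- **Asking for evidence is not foreign to the documents.** Protocol 10.3.3 wants facts or arguments for causality, not merely a relationship that cannot be excluded. That governs the investigator's causality rating, not AESI status, but the adjudication also asks about spread due to treatment.
- **The practical effect is limited.** Adjudication before unblinding limits differences between arms, though not omissions in all of them. SAP 5.8.1 plans no statistical comparison of safety data. Protocol 8.3.3 and 8.3.6 require AESIs to be followed up closely, in one centre, so unassessable events should be few.

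None of this answers the narrower point: the outputs, as described, do not separate events that were explained from events that could not be judged.

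**Conclusion.** The point holds as a minor matter of reporting. Ground 4 removes an event from the adjudicated remote-spread count without evidence against spread, under a standard that asks only whether spread is possible. Because the pre-adjudication table is not said to show reasons, the overview can show no remote-spread AESI when one was only unassessable, and a reader could not find that out from the tables.

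The size is 6.7 percentage points of an arm per affected participant. That rests on an assumed event: the documents give neither an AESI rate nor an expected number of unassessable events, and the true number may be zero. The restriction to confirmed events is explicit for the overview; for the AESI table by system organ class and preferred term, and for the AESI listing, it is only implied. The primary analysis, multiplicity procedure and power are unaffected.

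**What to change.** Amend SAP 5.8.3 in three places:

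1. Take insufficient information out of the exclusion grounds and make it a third adjudication outcome, so that each candidate is classed as confirmed possible spread, excluded with a documented reason (alternative cause, local effect or timing), or not assessable.
2. In the AE overview and the AESI table, report not-assessable events by arm, as participants and events, on a separate line beside the sponsor-confirmed count. The confirmed line keeps its meaning and the two are not merged. The sentence limiting the overview to confirmed events needs a matching change, and the SAP should say whether that limit also applies to the AESI table and listing.
3. Add the adjudication outcome and reason for exclusion to the pre-adjudication table.

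The cost is SAP and shell wording, plus recording the outcome of a review the sponsor already plans to do before unblinding. No new participant data are needed. The only downside is an AESI display that may look slightly less favourable.

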5.8.4 Vital Signs

A summary of the actual and change from baseline in each vital signs parameter by study intervention group and timepoint will be performed as well as a listing of vital sign data by study intervention group, with abnormal value highlighted. A listing of participants with Potentially Clinically Significant Abnormalities (PCSA) values as defined in [Appendix A5](#) will also be prepared. All data for a vital signs parameter will be displayed for a participant having at least one post-baseline PSCA value.

5.8.5 Physical Examination

The following summary and listings will be provided:

- A shift from baseline (normal vs abnormal) to end of study visit by study intervention group,
- A listing of physical examination data,
- A listing with any participants with at least one physical examination abnormality.

6 DATA HANDLING

6.1 Visit window

Time window (+/- 2 weeks) is used to calculate the protocol deviations defined as ICE for the analysis.

No other time windows are needed for analyses.

6.2 Unscheduled Visits, Retest, Withdrawal Visit,

All listings will include retests and unscheduled visits, while for the description by visit in the tables, only the scheduled visits according to the protocol will be described.

Unscheduled visit and retest measurements will be used to provide a measurement for a baseline data or endpoint value (e.g. worst value), if appropriate according to their definition.

If a value requires a retest (for vital signs) the closest non-missing reliable value to the scheduled visit will be used in the summary tables.

An assessment will be considered reliable if it is performed without any technical problem and if the result is within the range of likely values.

Participants who have withdrawn early from the study have their last assessment entered as visit 90 in the eCRF. By convention, for these participants, the visit number will be reassigned to the next empty visit number (i.e. if a participant has Visit 1, 2, 3 and 90 entered in the database, the visit number 90 will be reassigned to visit number 4) for summary tables.

6.3 Handling of COVID-19 Pandemic

Specific outputs will be provided as described in Ipsen's biostatistics recommendations for the "Management of COVID-19 pandemic related issues" to assess the impact of the COVID-pandemic as follows:

- Summary table with the number and percentage of participants exposed as well as impacted or infected and with the number of participants withdrawn due to COVID-19 with their reasons of withdrawal.
- Exposed participant is a participant ongoing at start of pandemic (January 03, 2020) or included during the pandemic phase (end of the pandemic not reached). Impacted participant is a participant who has been infected by SARS-CoV-2 or for whom the conduct of the study has been impacted (visit impacted; withdrawal related to COVID-19 pandemic). Participant infected are reported in SAEs.
- Summary table by visit with the number and percentage of participants having a visits impacted by COVID-19 with the type of impact and the reason(s) why COVID-19 pandemic impacted the visit.
- Summary table with the number and percentage of participants having a PDs due to COVID-19 Status by deviation category and listing of deviation due to COVID-19.
- Addition of "any Confirmed COVID-19 cases" in the overall summary table of AEs and listing of TEAEs including in the SMQ dedicated to COVID-19.
- Listing of COVID-19 tests.

7 DERIVED DATA (IF APPLICABLE)

Not applicable

9 APPENDICES

A1. Partial/Missing Date Convention

In all listings, missing or incomplete dates should be left as they have been recorded.

Algorithm for Prior/Concomitant

Medications, non-drug therapies, BoNT therapies and surgical procedures start and stop dates will be compared to the date of the first IMP administration to allow classification as either Prior only, Prior and Concomitant, or Concomitant only.

In case of partial start and/or stop dates, temporary date imputations will be done to determine the classification and derive the duration of occurrence:

- If a partial start date is reported, the first day of the month will be imputed for missing day and January for missing month,
- If a partial stop date is reported, the last day of the month will be imputed for missing days and December will be imputed for missing month.

In case incomplete start or stop date does not allow the classification, the occurrence will be classified as concomitant.

The duration of the occurrence will be calculated using the start and end date of the occurrence as end date – start date + 1. In case of partial start or end dates, the duration will be reported as “≤ xx” since at least one date is imputed and maximised.

In case of ongoing occurrence (e.g. at the end of the study or at the time of interim analysis if any):

- If the start date is complete, the duration will be reported as “≥ xx” and the date of end of study date or last attended visit will be considered as end date,
- If the start date is incomplete, the duration is not calculated.

Algorithm for Medical Histories

In case of partial start and/or stop dates, temporary date imputations will be done to determine the duration of occurrence:

- If a partial start date is reported, the first day of the month will be imputed for missing day and January for missing month,
- If a partial stop date is reported, the last day of the month will be imputed for missing days and December will be imputed for missing month.

The duration of the occurrence will be calculated using the start and end date of the occurrence as end date – start date + 1. In case of partial start or end dates, the duration will be reported as “≤ xx” since at least one date is imputed and maximised.

In case of ongoing medical history:

- If start date is complete, the duration will be “≥ xx” using the screening visit date and the start date of the medical history.
- If start date is incomplete, the duration is not calculated.

Algorithm for Adverse Events

For deriving the TEAE flag the following process of temporary date imputation is done (for AE start date only assuming no AE end date are missing). The date imputation algorithm for

incomplete adverse event start dates is described in [Table 3](#). Classification of adverse event according to its treatment-emergent status is then done using the imputed date.

In the following table, all dates are presented using an YYYY-MM-DD format. As an example, suppose First IMP administration = 2002-08-11 and several AEs have incomplete start dates.

Table 3: Data Imputation Algorithm for AE Start Date (ASTDT)

Description of incomplete date	Imputed numeric date	Example	
		Character date	Imputed date
Day is missing			
YYYY-MM < YYYY-MM of [First IMP admin.]	YYYY-MM-01	2002-07-XX	2002-07-01
YYYY-MM = YYYY-MM of [First IMP admin.]	Min ([First IMP admin.], AE end date)	2002-08-XX	Min (2002-08-11, AE end date)
YYYY-MM > YYYY-MM of [First IMP admin.]	YYYY-MM-01	2002-09-XX	2002-09-01
Day and month are missing			
YYYY < YYYY OF [First IMP admin.]	YYYY-01-01	2001-XX-XX	2001-01-01
YYYY = YYYY OF [First IMP admin.]	Min ([First IMP admin.], AE end date)	2002-XX-XX	Min (2002-08-11, AE end date)
YYYY > YYYY OF [First IMP admin.]	YYYY-01-01	2003-XX-XX	2003-01-01
Day, month, and year are missing			
XXXX-XX-XX	Min ([First IMP admin.], AE end date)		Min (2002-08-11, AE end date)

YYYY = non-missing year, MM = non-missing month, DD = non-missing day, XX = missing field.

If AE end date is partial, imputation could be done assuming the latest possible date (i.e. last day of month if day unknown, or 31st of December if day and month are unknown).

AEs duration will be calculated using the start and end date of the AE as end date – start date + 1. In case of partial start/end date the temporary imputed date will be used.

The duration of the AE will be calculated using the start and end date of the AE as end date – start date + 1. In case of partial start or end dates, the duration will be reported as “≤ xx” since at least one date is imputed and maximised.

In case of ongoing AE (e.g. at the end of the study or at the time of interim analysis):

- If start date is complete, the duration will be reported as “≥ xx” and the date of end of study date or last attended visit will be considered as end date.
- If start date is incomplete, the duration is not calculated.

A2. EudraCT categories for age

For EudraCT results summaries, in addition to quantitative descriptive statistics of age, demographic tables should include presentation of age using the following EudraCT categories (as applicable):

In utero
Preterm newborn - gestational age < 37 weeks
Newborns (0-27 days)
Infants and toddlers (28 days-23 months)
Children (2-11 years)
Adolescents (12-17 years)
Adults (18-64 years)
From 65 to 84 years
85 years and over

A3. Programming Convention for Outputs

All text fields must be left justified and numeric or numeric with some text specification (e.g.: not done, unknown, <4.5, ...) must be decimal justified.

The mean, median, lower quartile, upper quartile, SD, SE of the mean will be reported to one decimal place greater than the raw data recorded in the database.

The minimum and maximum values will be reported with the same number of decimal places as the raw data recorded in the database.

In general, the maximum number of decimal places reported should be four for any summary statistics.

Percentages will be presented to one decimal place. Percentages will not be presented for zero counts. Percentage will be calculated using n as denominator. The denominator n will be specified in a footnote for clarification if necessary. If sample sizes are small, the data displays will show the percentages, but in the CSR only frequency counts could be described.

P-values will be reported to four decimal places (e.g.: p=0.0037), after rounding. P-values which are less than 0.0001 will be presented as '<0.0001'.

Dates will be presented in the format [ddmmmyyyy] and times in the format [hh:mm].

A4. SAS code**a. MMRM analysis**

The SAS code for the MMRM is the following:

CCI

Where AVISITN includes all post-baselines visits when CMAP is measured, CMAPBL is the baseline of CMAP total amplitude and AVAL is the percentage relative to baseline of CMAP total amplitude (%).

If the PROC MIXED fails to converge, the first algorithm that leads to convergence in the following sequence of fallback measures will be the algorithm used for the primary analysis of the study:

- 1) Addition of scoring option

CCI

- 2) Addition of the no-diagonal factor analytic structure (via the TYPE=FA0(T) option of the REPEATED statement

CCI

- 3) Use of Toeplitz covariance structure

CCI

- 4) Use of compound symmetry covariance structure

CCI

CCI

CCI

5) ANCOVA model with covariates treatment and baseline CMAP amplitude

CCI

b. Exact (Clopper-Pearson) 95% confidence intervals for proportion

To obtain the exact (Clopper-Pearson) 95% CI for proportion of participants with recovery in each of the treatment arms, the following SAS code will be used:

CCI

c. Exact unconditional 95% confidence interval for the risk differences and Fisher's Exact Test

To obtain the exact unconditional 95% CI for the risk differences as well as the Fisher's Exact Test (right-sided, significance level 2.5%), the following SAS code will be used:

CCI

Where AVAL is recovery of CMAP amplitude, AVISIT is Week 28 or Week 40. Same model will be performed with TRTP in ("Dysport" "Xeomin").

CCI

A5. PCSA criteria for vital signs parameters

PCSA criteria for vital signs parameters are defined as follow:

Parameter	PCSA criteria
Systolic Blood Pressure	≤ 90 mmHg and change from baseline ≤ -20 mmHg ≥ 180 mmHg and change from baseline ≥ 20 mmHg
Diastolic Blood Pressure	≤ 50 mmHg and change from baseline ≤ -15 mmHg ≥ 105 mmHg and change from baseline ≥ 15 mmHg
Heart Rate	≤ 50 bpm and change from baseline ≤ -15 bpm ≥ 120 bpm and change from baseline ≥ 15 bpm
Weight	$\leq -5\%$ change from baseline $\geq 5\%$ change from baseline

A6. Listings conventions

Any listings will contain at least the following data: participant identifier, age and gender. When dates are presented, the associated study days should be included. They should be sorted by study intervention group then participant identifier.

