2.2 Benefit/Risk Assessment

This study will be conducted in healthy male participants. There is no benefit for this study population.

Risks inherent to the administration of BoNT are those related to distant spread from the site of administration. In clinical practice, the risk of occurrence of such undesirable effects may be reduced by using the lowest effective possible dose and by not exceeding the maximum recommended dose per indication as indicated in the respective product labels. Doses that will be investigated in the present study have been shown to safe and well tolerated, also associated with a lack of local diffusion to the adjacent muscles [[Pons 2019](#), [Wohlfarth 2007](#)].

There have also been occasional reports of hypersensitivity. This potential risk will be mitigated by appropriate selection of participants.

More detailed information about the known risks and reasonably expected adverse events may be found in the respective product labels for Dysport, Botox and Xeomin.

Safety will be closely monitored during the study. Type, severity, seriousness, duration, reversibility and outcome of treatment-emergent AEs (TEAEs) and adverse events of special interest (AESIs), a well as TEAEs leading to withdrawals will be followed. In addition, all AEs will be monitored by the sponsor to determine if they meet the criteria of AESIs.

2.2.1 *Risk Assessment of the Impact of COVID-19 Vaccination on Study Participants*

Currently there is no evidence of an increased safety risk in patients treated with BoNT prior to or following vaccination against COVID-19.

The doses of study intervention (BoNT) to be used in the study have been shown to be safe when injected into the EDB muscle. At 40 U, there is no local diffusion of Dysport into adjacent muscles. However, as a precautionary measure and to help minimise confounding factors in the safety assessments, a COVID-19 vaccine should not be administered within 7 days before or after the study intervention injection.

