8.3 Adverse Events (AEs) and Serious Adverse Events (SAEs), and Other Safety Reporting

The definitions of adverse events (AEs) and serious adverse events (SAEs) can be found in Appendix 10.3.

Adverse events will be reported by the participant (or, when appropriate, by a caregiver, surrogate, or the participant's legally authorised representative).

The investigator and any qualified designees are responsible for detecting, documenting, and recording events that meet the definition of an AE or SAE and remain responsible for following up all AEs (see Section 7).

The method of recording, evaluating, and assessing causality of AEs and SAEs and the procedures for completing and transmitting SAE reports are provided in Appendix 10.3.

8.3.1 *Time Period and Frequency for Collecting AE and SAE Information*

All AEs/SAEs will be collected from the signing of the ICF until EoS/EW visit at the time points specified in the SoA (Section 1.3).

Medical occurrences that begin before the start of study intervention but after obtaining informed consent will be recorded on the AE section of the case report form.

All SAEs will be recorded and reported to the sponsor or designee immediately and under no circumstance should this exceed 24 hours of awareness of the event, as indicated in Appendix 10.3. The investigator will submit any updated SAE data to the sponsor within 24 hours of it being available.

Investigators are not obligated to actively seek information on AEs or SAEs after conclusion of the study participation. However, if the investigator learns of any SAE, including a death, at any time after a participant has been discharged from the study, and he/she considers the event to be reasonably related to the study intervention or study participation, the investigator must promptly notify the sponsor.

8.3.2 *Method of Detecting AEs and SAEs*

Care will be taken not to introduce bias when detecting AEs and/or SAEs. Open-ended and non-leading verbal questioning of the participant is the preferred method to inquire about AE occurrences.

8.3.3 *Follow-up of AEs and SAEs*

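### In three rows of SAP Appendix A1, Table 3, the imputed adverse event start is not the earliest possible date, so the duration printed as an upper bound can be too short

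*SAP*

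**What the plan says.** SAP Appendix A1, Algorithm for Adverse Events, gives Table 3 one purpose: "For deriving the TEAE flag the following process of temporary date imputation is done", applied "for AE start date only assuming no AE end date are missing". Four of its seven rows impute the first day of the month or 1 January. The other three impute "Min ([First IMP admin.], AE end date"), that is, whichever of the two dates is earlier. Those three are day missing with the dosing month, day and month missing with the dosing year, and everything missing.

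Two paragraphs on duration follow. The first gives end minus start plus one and adds "In case of partial start/end date the temporary imputed date will be used". The second repeats the formula and says that, with a partial start or end, the result is shown as ≤ xx "since at least one date is imputed and maximised". A partial end date may be set to its latest possible value. An ongoing event with an incomplete start gets no duration.

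The same appendix uses the ≤ wording for medications and for medical history, where a partial start goes to the first of the month or to January. SAP 5.1.4 says that durations tied to partial or missing event dates will be presented from the Appendix A1 imputations.

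Protocol 8.3.1 states: "All AEs/SAEs will be collected from the signing of the ICF until EoS/EW visit". The Schedule of Activities (Protocol 1.3) places screening on Day -14 to Day -1.

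**The concern.** A ≤ sign tells the reader that the event cannot have lasted longer. That is true only if the imputed start is the earliest date compatible with the record and the end is the latest. The earlier of injection date and end date is a sensible cautious choice for the TEAE flag, because it keeps a doubtful event on the treatment-emergent side. It is not the earliest possible start. The ≤ wording is correct for medications and medical history, but the AE algorithm attaches it to a start rule that does not support it.

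The situation can arise, because events are collected from consent, before dosing. At stake is the accuracy of a presented safety figure. Any error runs one way: the event looks shorter than it may have been, under a sign that rules out anything longer. Protocol 2.2 names duration among the event attributes to be followed ("Type, severity, seriousness, duration, reversibility and outcome of treatment-emergent AEs").

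**Working it through.** **Inputs.** Injection date 2002-08-11 (the SAP's example, Appendix A1). Duration = end − start + 1 (Appendix A1). Earliest consent is Day -14 (Protocol 1.3), which is 2002-07-28 for this injection date.

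**Reproducing Table 3.** Applying the seven rows to the SAP's example dates, with an end date well after dosing, gives 2002-07-01, 2002-08-11, 2002-09-01, 2001-01-01, 2002-08-11, 2003-01-01 and 2002-08-11. These match the table.

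**The three rows, complete end date.**

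| Recorded start | End | Imputed start | Printed | Earliest start the record allows | Longest possible |
|---|---|---|---|---|---|
| 2002-08-XX | 08-05 | min(08-11, 08-05) = 08-05 | ≤ 1 | 08-01 | 5 − 1 + 1 = 5 |
| 2002-08-XX | 08-20 | min(08-11, 08-20) = 08-11 | ≤ 10 | 08-01 | 20 − 1 + 1 = 20 |
| 2002-XX-XX | 08-20 | 08-11 | ≤ 10 | 07-28 (consent on Day -14) | 4 days in July + 20 = 24 |

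The possible shortfalls are 4, 10 and 14 days. In the first line the imputed start equals the end date, so any event in these rows that ended before dosing prints ≤ 1.

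**How far the failure extends.** All true starts from Day -14 to Day -1 were crossed with all true lengths from 1 to 60 days (14 × 60 = 840 combinations), end date complete. The counts describe this grid and are not probabilities.

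- Day missing: the bound fails in 590 of 840, by at most 10 days. The 590 are the ten August starts times 60 lengths, less the ten one-day events. The four July starts fall in a first-of-month row and never fail.
- Month missing, or everything missing: it fails in 826 of 840 (840 less the 14 one-day events), by at most 14 days.
- True starts from the injection date up to 279 days after it: no failures in 16,800 combinations.

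**Cases where the bound holds.**

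- First-of-month row: recorded 2002-07-XX, true 07-29 to 08-20. Printed 31 + 20 = ≤ 51; true 3 + 20 = 23.
- Partial end: true 08-03 to 09-05, recorded 2002-08-XX to 2002-09-XX. The end goes to 09-30, so the printed figure is 21 + 30 = ≤ 51; true 29 + 5 = 34. With the day of the end date missing throughout, failures on the same grid drop to 109 of 840 (day of start missing) and 201 of 840 (month of start missing, or everything missing).

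**The case against.** The best case against raising this is that it hardly matters. SAP 5.8.3 plans participant counts, event counts and listings, and names no table or test of AE duration. Appendix A1 leaves incomplete dates in listings as recorded, so a reader would see the partial date beside the figure. There are 45 healthy participants at one centre, AEs are recorded at both screening and baseline, and missing data are queried, so few records should qualify. The days that can be lost all lie before injection; the time from injection to the end of the event is counted in full. All of this stands, and it makes the point small. It does not make the inequality correct, and SAP 5.1.4 commits to presenting durations built this way.

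Three stronger readings are tempting, and the documents do not support them.

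- *Every event with a partial start that began before dosing has a false bound.* Four of the seven rows give valid bounds, and a partial end set to its latest value can restore the bound in the other three.
- *A treatment-emergent event that qualifies by worsening is always printed too short.* SAP 5.8.3 includes "Events whose intensity increased on or after the date and time of IMP administration", but does not say which start date such a record carries. Protocol 10.3.1 counts an exacerbation of a pre-existing condition as an AE in its own right, so the record might start at the worsening.
- *The two duration paragraphs contradict each other.* One says which date enters the formula, the other how the result is printed. Both can be followed together.

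**Conclusion.** The point holds in a limited form. In three rows of Table 3, an event with a complete end date and a true start before the imputed start is given an upper bound that is too short. The shortfall is at most about the 14-day screening window: 10 days (day missing) or 14 days (month or everything missing) with the SAP's example injection date. This assumes that no AE starts before consent and that consent is no earlier than Day -14. The number of affected records cannot be known in advance and is probably small.

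Only presented durations are affected. A reader might infer that post-injection event time is hidden or that safety counts are biased. Neither follows: the flag uses Table 3 as intended, and no AE count or pharmacodynamic analysis uses duration. The ≤ 1 case concerns events over before dosing, which are not treatment-emergent, so the Protocol 2.2 statement on TEAE duration does not reach them. This is a minor but definite error in a stated rule.

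**What to change.** State in Appendix A1 that Table 3 serves the TEAE flag only, and remove the sentence that carries the temporary imputed date into the duration. For duration, set a partial or missing start to the earliest date the record allows, not before the date of informed consent, and a partial end to the latest possible date; then report ≤ xx.

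The consent floor matters. Without it, 2002-XX-XX ending on 08-20 would run from 1 January and print ≤ 232, against ≤ 24 with consent on 07-28, and a fully missing start would have no earliest date at all.

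At a minimum, drop the ≤ sign and the claim of maximisation for the three rows.

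The cost is a short wording change in the SAP and one extra derived date in the AE dataset. The downside is that some printed bounds become longer. No flag, count or pharmacodynamic result changes.
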